Pain intensity: Self-report of pain is recognized as the gold standard for pain assessment given the inherently subjective nature of pain. Although the numeric rating scale (NRS), verbal rating scale (VRS), and the visual analogue scale (VAS) are all reliable and valid measures of pain, there are differences that led to the IMMPACT recommendation and our selection of the NRS as the primary measure of pain. Of particular note is the fact that the NRS is the accepted measure for screening for the presence and intensity of pain for the VHA, and it is quite familiar to Veterans. Data from several studies suggest that use of this measure, relative to the VRS and VAS, yields fewer missing observations and is preferred by more participants, especially among older persons and among those prescribed opioids.³¹ The NRS can be easily administered by either a research assistant, via the telephone, or online as is proposed for this study. In this trial, participants will be asked, "Please rate your pain by indicating the number that best describes your average pain in the last 24 hours on a 0 (no pain) to 10 (pain as bad as you can imagine) scale".³² A clinically-meaningful reduction in pain intensity will be defined as a reduction in pain of 30% on the NRS relative to baseline NRS. This threshold is also consistent with IMMPACT recommendations based on an analysis of ten studies that examine changes in absolute ratings of pain intensity and independent ratings of treatment satisfaction.³³

Emotional functioning: Overall functioning will be assessed using the 65-item Profile of Mood States (POMS), a multidimensional measure of emotional functioning designed to assess six dimensions of mood and can be used in non-psychiatric or physically ill populations.³⁴ Internal consistency (0.84 to 0.95, depending on subscale) and test-retest reliability (0.65 to 0.74, depending on subscale) is good. Depressive symptom severity will be assessed using the 21-item Beck Depression Inventory (BDI) a widely used self-report measure with excellent internal consistency (.92) and stability (.80-.90).³⁵ Both measures were recommended by IMMPACT.²⁶

Fatigue: Clinical fatigue will be assessed using the Multidimensional Fatigue Inventory (MFI).³⁶ The MFI can be scored to produce 5 dimensions: general fatigue, physical fatigue, mental fatigue, reduced motivation, and reduced activity.

Sleep Problems: Sleep problems will be assessed using the MOS Sleep Scale. The MOS is segregated into subscales addressing seven sleep domains (i.e. sleep disturbance, snoring, awaken short of breath or with headache, adequacy of sleep, somnolence, a problems index 1 and a problems index 2). An additional single item assesses quantity of sleep.³⁷

Behavioral Goal Adherence: Goal adherence for previous week's goals will be assessed via telephone on a weekly basis for 10 weeks post-baseline using a 0-10 Likert scale, where 0 indicates no adherence to completing the goal and 10 indicates complete adherence.

Tertiary outcomes:

Module completion: Participants will be asked during weekly (for 10 weeks) phone calls placed by the study staff about completion of modules (i.e., how many modules completed, which modules) during the previous week. In addition, the web developer will build a database to track time spent on each module, which modules were accessed, and number of times each participant accessed the program. This database will be linked only to userID and will not be linked with PHI.

Module usability: Participants will be asked during weekly phone calls about usability of modules. Specifically, they will be asked to rate each completed module on a 0-10 scale where 0= very difficult and 10=very easy, in terms of accessing information presented, understanding information presented, setting a module goal, navigating the module.

Treatment credibility: Participants' judgments of treatment credibility will be assessed at the post-baseline assessment interval using a questionnaire adapted from Borkovec and Nau.³⁸ This measure has been shown to have an internal consistency of .85 and test-retest reliability of .83.

Patient satisfaction: Patient satisfaction will be assessed by the Pain Treatment Satisfaction Scale which is a 5-item satisfaction survey designed to assess patient satisfaction with 5 domains of pain care.³⁹ This measure shows good internal consistency (.83-.90 across two samples) and significant associations to follow-up treatment satisfaction and staff and patient ratings of patient improvement.

VPMRC program-specific feedback: Participants will be administered an investigator-created measure designed to assess the layout of the website, ease of navigation, relevance of the materials presented, appeal of the program, understanding of key concepts, appropriateness of the graphics and multimedia interface, ease of use, problems encountered, amount of material presented, and general likes and dislikes

Sociodemographic status and pain-relevant variables: Participants' age, sex, education level, racial/ethnic background, and marital status will be assessed at the time of the baseline examination. Pain-specific factors such as pain duration, number and location of pain sites, past and current pain treatments, cause of pain, and presence of radicular symptoms, will also be assessed at baseline.

Pain medication: At baseline, medication use will be assessed by the study coordinator through participant interview and VACHS computer pharmacy records. Medications will be coded into several categories, namely non-steroidal anti-inflammatory, non-opioid analgesics, opioid analgesics, and benzodiazepines and other sedative/hypnotics using a recording sheet used in our prior studies. The specific medication used, its dose, and schedule of administration will be recorded. At 10 weeks post-baseline, this information will again be collected via patient self-report using Trial DB, and participants' medical records will be independently reviewed for changes in medication regimen from baseline by the RA for corroboration.

Analytic Plan

Because the overall goal of the project is to develop a pain self-management resource for Veterans, the VPMRC, we will employ an iterative process of formative evaluation through two distinct Phases in order to optimally revise and modify the VPMRC. All analyses will be conducted in the service of further refining and optimizing the usability and effectiveness of the program. Ultimately, these data and the subsequent modifications to the VPMRC will produce a resource that can be submitted to examination of efficacy through a randomized controlled trial.

Phase I: Development of the VPMRC

Using the Think Aloud protocol, qualitative data will be collected regarding participants' verbal, audio-recorded feedback of their experiences with navigating the VPMRC homepage, self-assessment, resources, and reviewing the treatment modules. Consistent with a phenomenologic approach (i.e., capturing the essence of the participant's experience), the qualitative feedback collected from each of the two study visits for each participant will be transcribed, coded, and systematically analyzed for emerging themes. These analyses will be shared with members of the EP and will be used to inform modification of

the VPMRC with respect to the layout of the website, ease of navigation, relevance of the materials presented, appeal of the program, understanding of key concepts, appropriateness of the graphics and multimedia interface, ease of use, problems encountered, amount of material presented, as well as general likes, dislikes, overall functionality of the program, and recommendations for change.

Quantitative data collected from the Post-intervention Measure will provide information regarding the usability, ease of navigation, and functionality of the program and specific modules. Descriptive statistics (e.g., means, standard deviations, frequencies) will be calculated for these data.

All quantitative and qualitative data collected, with input from members of the EP, will be used to guide modification of the VPMRC to reduce identified issues with navigation of the site, graphics and audio effects, relevance of materials for the population, ease of use with respect to the self-assessment, homepage functions, and other related issues. These changes will be made prior to initiating the pilot feasibility trial described in Phase II.

Phase II: Pilot Feasibility Trial of VPMRC

We will analyze the primary and secondary hypotheses according to the Intent-to-Treat principle. If missing data are minimal (e.g., <5%), we will conduct a complete case analysis; otherwise, imputation methods will be used to fill in the missing values. Several imputation approaches will be considered after inspection of the missing data rates and before any analyses of treatment effects are conducted. These approaches would include imputing the worst and best value (i.e., bounds on the treatment effects) and using multiple imputation assuming missing at random. These approaches would be supplemented by sensitivity analyses assuming nonignorable missingness. Only pre-specified baseline variables that may affect the outcome will be considered as adjustment variables in a sensitivity analysis. These variables include age, race/ethnicity, gender, educational attainment, and depressive symptom severity.

The primary endpoint is the mean difference in baseline to post-baseline follow-up scores on the primary measure of pain interference (i.e., WHYMPI-Interference Scale) at 10 weeks post-baseline. T-tests will be utilized to evaluate the effect of treatment on the primary outcome, and an ordinary least squares regression model will be used to control for potential confounders. The treatment will be represented by an indicator variable. The model fit will be assessed using graphical techniques and regression diagnostics. In a sensitivity analysis, we will examine the effect of treatment adjusted for the pre-specified set of baseline covariates. Analyses of covariance (ANCOVAs) will be employed to control for differences among participants in baseline scores and to determine whether participant characteristics are associated with changes in scores on outcome variables across time.

Because the primary and secondary hypotheses test differences in outcome measure scores across time, we will use paired t-tests, or their non-parametric analogs (e.g., Mann-Whitney test) to compare mean (or median) scores on the outcomes across time. Given the multiplicity of tests for secondary outcomes (i.e., six outcomes) and the power of the study, in addition to maximizing sample size, we will use the Bonferroni procedure p-value, which we conservatively estimate to be $p = 0.008$, based on an overall significance of $p = 0.05/6$, to account for the number of comparisons. Our six secondary outcomes will be examined with the purpose of informing future modifications to the VPMRC and additional hypothesis generation. We have not grouped within subsets in order to ensure a more conservative approach. Tertiary hypotheses will examine data related to usability (use of and functionality) and satisfaction (satisfaction, credibility) with the VPMRC and will be collected only at 10 weeks post-baseline. Descriptive statistics will be employed to examine these data in order to describe participants' experiences with the VPMRC.

As in Phase I, quantitative data from the Post-intervention Measure with added data from the weekly phone calls for Phase II regarding usability of and satisfaction with the VPMRC will be used to modify the program. In addition, we will use specific primary and secondary outcomes data to inform modification of the VPMRC. For instance, if the data suggest a significant reduction in pain interference, but more modest changes in fatigue or depression, specific modules, such as Pacing (the pleasant activity scheduling coping skill) or Adaptive Stress Response (the using positive coping statements coping skill) will be targeted for further content and presentation enhancement to increase benefit to patients on these important related outcomes. We will also use data from tertiary outcomes to further modify presentation of the various treatment modules. For example, if certain modules are clearly preferred, as indicated by participant report of modules completed and satisfaction with the modules, other, less-preferred modules may be further enhanced (e.g., changes to audio-visual aspects, presentation of content within modules) to increase use, interest, and satisfaction.

6. References:

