The primary aim of this phase of the project is to execute a pilot feasibility trial to evaluate the preliminary efficacy of, usability of, and satisfaction with the VPMRC. A single treatment condition (Usual Care [UC] plus VPMRC) X two evaluation periods (baseline and 10 weeks post-baseline) design with multiple dependent measures will be employed. Participants in the study will be 55 Veterans with CLBP. Participants will continue to receive care as usual from their primary care providers (PCPs) and other healthcare providers.

Recruitment

VistA Search: We will identify potential Veterans for inclusion from available electronic medical record (EMR) data in VistA. All Veterans 18 years or older from VACHS (Station 689) with low back pain defined using the *International Classification of Diseases, Ninth Revision* diagnostic codes related to low back pain (724, 7240x, 7241x, 7242x, 7243x, 7244x, 7245x, 7246x, 7247x, 8460x, and 8472x) will be considered eligible. We will attempt to oversample OEF/OIF/OND, female, and minority Veterans, as these Veterans have high prevalence rates of chronic musculoskeletal pain conditions and are of particular interest in the context of the proposed study. We will then identify Veterans in this group to exclude psychiatric hospital admissions in the previous 30 days, suicide flag in the Electronic Medical Record (EMR), or behavioral alert flag in the EMR.

A letter will be sent to the identified Veterans from their PCPs informing them about the study and inviting them to participate. Veterans will be provided with information about the voluntary nature of the study and the option to "opt out" from further contact with study staff by notifying us of their lack of interest by phone, email or letter. Veterans who do not contact us will be called by the study RA to be further informed about the study and, if interested, to be screened for participation. Screening will include several of the key eligibility criteria for the study (e.g., confirmation of presence of CLBP, readiness to engage in self-management for pain, interest in Internet-based pain care, and absence of medical and psychiatric comorbidities). If screening suggests potential eligibility, and if the Veteran is interested, an in-person appointment for obtaining written informed consent and baseline assessment data will be scheduled. Solicitation letters will be mailed in waves in order to prevent overwhelming our capacity to offer participation in a timely manner.

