
We also will post the already approved flyer in the following venues: 1) patient care waiting areas, 2) flat screen informational televisions around the hospital, 3) Good Morning VA Connecticut 4) VA Connecticut's Facebook page, 5) vet centers (after securing their permission) and 6) at the Pain Education table. We also will provide advertisement language in "The Prime Times", a PRIME Center community newsletter.

Procedures

Veterans meeting eligibility criteria based on screening (e.g., by phone) will be scheduled to meet in person with the RA to obtain written informed consent and to complete all baseline study measures. Immediately upon completing the measures, the participant will meet separately with the study coordinator to receive instructions for accessing the VPMRC, and additional logistical details related to their participation in the study. Participants will be provided with a userID and temporary password for accessing the VPMRC program.

Questionnaires and inventories that comprise the principle outcome measures will be reassessed at 10 weeks post-baseline, online using a secure, encrypted Internet-based interface called TrialDB. TrialDB allows participants to complete the self-report questionnaires via their home computer without the need to travel to VACHS. This system has been successfully used to collect data in the HSR&D funded "Women Veterans Cohort Study" (WVCS; PI: [name]). The RA and TrialDB data manager will check the TrialDB reports for accurate and timely completion. The RA will contact participants by phone or email at 10 weeks post-baseline to prompt them to complete post-baseline measures online. If participants are unable to complete the assessments online using TrialDB, alternative arrangements for data collection will be made, such as administering the measures to the participant in person or mailing the measures to the participant with a postage-paid return envelope. The 10 weeks post-baseline timeframe was chosen to allow sufficient time to complete the tailored skills modules and will serve as the post-intervention assessment. Table 4 outlines specific assessment measures to be collected at each assessment point. Participants will be paid \$75 for their participation in each of the two assessments.

Table 4. Phase II Assessment Schedule

	Baseline in-person	Weekly Telephone	10 weeks Post- baseline TrialDB
Regular computer/Internet access	X		
Readiness to Change Checklist	X		

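### By default the outcome scales are completed in person at baseline and online at home at week 10, so in this one-arm trial mode and setting are largely confounded with time and may bias the primary change

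*Combined protocol and SAP*

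**What the plan says.** The Phase II Design section describes "A single treatment condition (Usual Care [UC] plus VPMRC) X two evaluation periods (baseline and 10 weeks post-baseline) design", and adds: "Participants in the study will be 55 Veterans with CLBP".

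Under Procedures, eligible Veterans "will be scheduled to meet in person with the RA to obtain written informed consent and to complete all baseline study measures". The principal outcome questionnaires "will be reassessed at 10 weeks post-baseline, online using a secure, encrypted Internet-based interface called TrialDB". The stated advantage is convenience: "TrialDB allows participants to complete the self-report questionnaires via their home computer without the need to travel to VACHS". For participants who cannot complete the forms online, other arrangements are allowed, "such as administering the measures to the participant in person or mailing the measures to the participant with a postage-paid return envelope".

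Table 4 builds the difference into its columns. The first is headed "Baseline in-person" and the last names TrialDB at 10 weeks. WHYMPI-Interference, the pain intensity NRS, POMS, BDI, the fatigue scale and the MOS Sleep Scale are marked in both.

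The Analytic Plan defines the primary endpoint as the mean change in WHYMPI-Interference from baseline to 10 weeks and compares scores over time with paired t-tests or a non-parametric analog. The adjustment variables are age, race/ethnicity, gender, education and depressive symptom severity. Mode of completion is not among them, has no sensitivity analysis, and is not named as a limitation.

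**The concern.** The trial has two measurement occasions and one group. If Veterans report differently in the presence of study staff than alone at a home computer, the difference is added to the pre-post change. In a randomized trial a mode effect common to both arms would cancel; here nothing cancels it.

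At stake is the reading of the primary result and of the secondary scales collected the same way. A shift unrelated to the VPMRC could help produce a significant improvement, or mask part of a real one. These results are also meant to guide which modules are revised. The week-10 fallback adds a smaller problem: mode can differ between participants at follow-up, and the plan does not say how this is handled.

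**Working it through.** The plan states no mode effect and no SD of change, so there is no figure to reproduce. The calculation shows only how sensitive the primary test would be.

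**Inputs**
- From the documents: n = 55 (Design); meaningful reduction on WHYMPI-Interference 0.6 points (Outcome Measures); paired t-test (Analytic Plan).
- Assumed: two-sided alpha 0.05 for the primary test (neither sidedness nor the primary alpha is stated); SD of change s = 1.0, 1.2 or 1.5; constant mode shift b = 0, 0.1 or 0.2 points towards improvement; no true change.

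**Step 1. Smallest mean change that is significant.** SE = s/√55 and the critical t on 54 df is 2.005.
- s = 1.0: SE = 0.135, threshold 2.005 × 0.135 = 0.27
- s = 1.2: SE = 0.162, threshold 0.32
- s = 1.5: SE = 0.202, threshold 0.41

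All three lie below 0.6.

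**Step 2. Chance of a significant improvement with no true change.** This is P(T > 2.005), where T is noncentral t on 54 df with noncentrality b/SE. Only the improvement direction is counted, so the reference value is 2.5%.

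| Mode shift b | s = 1.0 | s = 1.2 | s = 1.5 |
|---|---|---|---|
| 0 | 2.5% | 2.5% | 2.5% |
| 0.1 | 10.9% | 8.8% | 7.0% |
| 0.2 | 30.8% | 22.8% | 16.1% |

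**Step 3. Chance that the observed mean reduction reaches 0.6 with no true change.** By normal approximation this is P(Z > (0.6 − b)/SE). For b = 0.2:
- s = 1.0: 0.4/0.135 = 2.97, giving 0.2%
- s = 1.5: 0.4/0.202 = 1.98, giving 2.4%

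**Step 4. A true change below the threshold.** Suppose the true mean reduction is 0.4 and b = 0.2. The expected observed reduction is 0.4 + 0.2 = 0.6, so the chance of reaching 0.6 is 50%. Without the shift it is P(Z > 0.2/SE): 7% for s = 1.0 and 16% for s = 1.5.

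**Step 5. Does the fallback help?** If a share f of follow-ups were in person, the mean shift would fall to (1 − f) × b. For an assumed f = 10% and b = 0.2 this is 0.9 × 0.2 = 0.18. Nor could those cases measure the mode effect. With 6 of 55 in person, the 95% half-width of the contrast is 2.006 × s × √(1/6 + 1/49), which is 0.87 points for s = 1.0 and 1.30 for s = 1.5. Those participants would also be self-selected.

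**The case against.** **The documents give no evidence of a mode effect.** This stands. Neither size nor direction is given, so a reader may infer that the change score is biased, but the text supports only that it may be.

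**Mode is not fully confounded with time.** This stands as a matter of wording. The fallback allows "administering the measures to the participant in person or mailing the measures to the participant with a postage-paid return envelope", so not every participant need change mode. Mode is confounded by default. The fallback does not solve the problem (Step 5).

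**The change of medium is partly inferred.** This also stands. Procedures does not say whether baseline forms are on paper, on a computer or read out. The pain intensity text mentions online administration without tying it to a visit. No location is named for the Phase II baseline, although the remark about avoiding travel to VACHS suggests one. If baseline were already completed in TrialDB, staff presence and setting would still differ, and the protocol should say so.

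**A plausible shift could not manufacture a clinically meaningful result.** Largely right for a 0.2-point shift acting alone (Step 3). It does not cover a true change somewhat below 0.6 (Step 4) or the significance test (Step 2).

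**This is a pilot.** The Analytic Plan leaves the examination of efficacy to a later randomized trial, and a one-arm change could not be attributed to the VPMRC even with identical modes. Home completion is also a reasonable way to spare travel. This limits the consequence. But preliminary efficacy is a stated aim, and unlike natural course or regression to the mean, the mode part can be removed without a control arm.

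**Conclusion.** The point holds in a limited form. By default, mode and setting both change between the only two assessments of a one-arm trial, and the plan neither standardizes nor analyzes mode. Any resulting effect may bias the primary change in either direction, by an amount the trial cannot separate from change over time.

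Under the stated assumptions, a shift of 0.1 or 0.2 points towards improvement raises the chance of a significant improvement from 2.5% to 7–11% or 16–31%. A 0.2-point shift alone reaches a 0.6-point mean reduction in only 0.2–2.4% of trials, though it can carry a true change somewhat below 0.6 up to the threshold. Both the shift and the SD are assumptions; a shift of zero is possible.

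The documents do not support concluding that the result is biased, that every participant switches mode, or that staff read the baseline questions aloud. This is a cheap improvement to a pilot, not a flaw that invalidates it.

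**What to change.** 1. In Procedures and Table 4, have participants self-complete the baseline outcome measures in TrialDB during the existing baseline visit, and state the medium and the research assistant's role.
2. Record the mode actually used at each assessment (TrialDB, in person or mail).
3. In the Analytic Plan, add a sensitivity analysis of the primary endpoint restricted to participants with the same mode at both times.
4. Report the remaining visit-versus-home difference as a limitation, because step 1 does not remove it.

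The cost is small: TrialDB is already needed for week 10, so this is a procedural edit, one recorded item and one extra analysis. Some participants may need help with the computer at the visit. The sensitivity analysis drops a probably small, self-selected group, so it should support the main analysis and not replace it.

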The primary aim of this phase of the project is to execute a pilot feasibility trial to evaluate the preliminary efficacy of, usability of, and satisfaction with the VPMRC.

The primary hypothesis is that a clinically meaningful reduction in pain interference with functioning post-exposure to the VPMRC will be observed compared to baseline ratings.

The secondary hypothesis is that Veterans who participate in the VPMRC will report a clinically meaningful reduction in pain intensity and statistically significant improvements on other important

problems commonly associated with CLBP including fatigue, sleep problems, depressive symptoms and negative mood, relative to baseline.

The tertiary hypothesis is that participants will report high levels of interest (credibility), use, and satisfaction with the VPMRC.

3. Background:

Limitations of current interventions for CLBP

For years, the practice of pain medicine has over-emphasized expensive and modestly effective treatments for CLBP, while under-utilizing inexpensive evidence-based behaviorally-oriented approaches that have demonstrated comparable or superior effect.^{1,2,3,4,5} Non-pharmacological treatments such as education, exercise, and behaviorally-based therapies have been demonstrated to be efficacious and effective, but are rarely used in routine clinical practice. Optimal care should combine both pharmacological and non-pharmacological behavioral interventions – but again, this is rarely done. Patients have historically considered behavioral interventions to be “mental health” resulting in reluctance to accept the need for a “psychological” treatment for their pain. It is imperative that a viable delivery platform be developed to facilitate Veteran access to efficacious non-pharmacological interventions. Such integrated delivery has become the “gold standard” of care for other chronic medical conditions such as diabetes, congestive heart failure, and asthma. The development of the Veterans Pain Management Resource Center (VPMRC) represents a necessary “first step” in providing comparable evidence-based disease management for CLBP – a long anticipated transformation in how clinical pain medicine is practiced.

Behavioral interventions for pain self-management

Cognitive-behavioral therapy

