Usual Care (UC): All participants will continue to receive whatever pain care they have been receiving. There will be no attempt by study personnel to influence ongoing pain care. Although it is beyond the scope of this project to influence pain care at VACHS, it may be important to know that VACHS continues to work to implement the VHA's stepped care model and to ensure that accepted standards for pain assessment and treatment are met for all Veterans. Within the primary care setting, a Primary Care Pain Workgroup works to promote system improvements related to pain care. Facility performance improvement data document a high rate of adherence to performance criteria related to documentation of pain assessments, treatment plans, and reassessment of the effectiveness of the interventions. Participants in this study will be encouraged to discuss pain concerns with their PCP. Results from the Stepped Care for Affective Disorders and Musculoskeletal Pain (SCAMP) trial conducted in both VHA and non-VHA settings and involving a collaborative care intervention for improving pain outcomes indicated that spill-over for pain outcomes are likewise minimal.²⁷ Whatever minor spillover does occur, results in a conservative estimate of the intervention's efficacy.

Veteran Pain Management Resource Center (VPMRC): Participants will continue to receive UC as described above, in addition to receiving access and being encouraged to complete the VPMRC program. The VPMRC will be accessed via the Internet at the participant's home or other regular access point. The VPMRC will guide participants in initially completing a self-assessment screening tool for module selection and in setting personally-relevant goals, in addition to assisting them with tracking progress made toward goal accomplishment. The skill modules identified by the self-assessment will be listed and available to the patient to access, learn, and practice through written text, guided narration, video demonstration, and interactive printable action plans to assist patients in learning and practicing

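### The protocol calls spillover bias conservative and labels the result a treatment effect, but a single-arm pre-post comparison supports neither statement

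*Combined protocol and SAP*

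**What the plan says.** The Phase II Design section sets "A single treatment condition (Usual Care [UC] plus VPMRC) X two evaluation periods (baseline and 10 weeks post-baseline) design" in 55 Veterans. The primary hypothesis under Purpose is that a clinically meaningful reduction in pain interference "post-exposure to the VPMRC will be observed compared to baseline ratings". The Analytic Plan for Phase II defines the primary endpoint as the mean baseline-to-10-week difference on the WHYMPI-Interference Scale and specifies paired tests across time.

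The Usual Care paragraph of the Intervention Description says that ongoing pain care continues, that study staff will not try to influence it, and that participants will be encouraged to raise pain concerns with their primary care provider. It cites another trial for the view that spillover is minimal and concludes: "Whatever minor spillover does occur, results in a conservative estimate" of the intervention's efficacy.

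The Phase II analytic plan uses treatment-effect language four times:

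- "before any analyses of treatment effects are conducted" (timing of the imputation decision)
- "bounds on the treatment effects" (worst- and best-value imputation)
- "T-tests will be utilized to evaluate the effect of treatment on the primary outcome" (primary test)
- "we will examine the effect of treatment adjusted for the pre-specified set of baseline covariates" (sensitivity analysis)

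Of the least-squares model, which is meant to control for confounders, it adds: "The treatment will be represented by an indicator variable".

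**The concern.** Spillover is conservative in a two-arm trial because it improves the control arm and shrinks the difference between arms. Phase II has no control arm. Here improvement from usual care adds to the observed change, which is the opposite of what the sentence says.

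Preliminary efficacy is part of the Phase II primary aim. A reader who accepts the word conservative would treat the pilot change as a lower bound when deciding on or planning the later randomized trial. The analytic plan reinforces that reading by naming the change a treatment effect and by suggesting that regression can control for confounding.

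**Working it through.** **Step 1: what the estimate contains.** The plan gives no figure to reproduce here; the check is an identity. With one arm,

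expected pre-post improvement = VPMRC effect + all other change over 10 weeks.

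The documents point to several possible contributors to the second term: changes in usual care (the facility is still implementing stepped care, and participants are encouraged to speak to their provider), weekly staff calls, and assessment in person at baseline but online at week 10. Natural course and regression to the mean may add to it.

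Illustration with an assumed VPMRC improvement of 0.3 points:

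- background improvement of 0.3: 0.3 + 0.3 = 0.6 observed (overstated)
- background worsening of 0.3: 0.3 − 0.3 = 0 observed (understated)

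The bias can have either sign.

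**Step 2: the treatment indicator.** The plan does not state the data layout.

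- *One change score per participant.* The indicator is 1 for everyone and duplicates the intercept. Intercept, indicator and the five pre-specified covariates (one column each) make 7 columns; a simulated data set with n = 55 gave rank 6. The indicator cannot be estimated.
- *Two rows per participant.* The indicator is 0 at baseline and 1 at week 10. It can be estimated, but it is the time variable and carries the same uncontrolled change.

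**Step 3: baseline adjustment.** Regress the change D on covariates X centred at their sample means. By least squares,

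intercept = mean(D) − b′ × mean(X − mean(X)) = mean(D) − 0 = mean(D).

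In complete cases the adjusted mean change at the sample covariate means therefore equals the unadjusted one; the simulated difference was 5.6e-17, zero to rounding. Adjustment may change the standard error, but it cannot remove background change.

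**Step 4: how far background change alone could go.** This illustrates uncontrolled change in general; it does not measure the harm of the spillover sentence. Assumptions, none from the documents: VPMRC effect 0, background improvement 0.2 points, SD of change 0.6 to 1.2, two-sided 5% primary test, and 44 completers as an alternative to all 55. The rejection probability comes from the noncentral t distribution with noncentrality 0.2/(SD/√n). The smallest significant mean change is t(0.975, n−1) × SD/√n.

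| SD of change | P(significant), n=55 | P(significant), n=44 | Smallest significant change, n=55 | Smallest significant change, n=44 |
|---|---|---|---|---|
| 0.6 | 0.680 | 0.580 | 0.162 | 0.182 |
| 0.8 | 0.445 | 0.368 | 0.216 | 0.243 |
| 1.0 | 0.308 | 0.254 | 0.270 | 0.304 |
| 1.2 | 0.229 | 0.191 | 0.324 | 0.365 |

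**Step 5: the plan's own yardstick.** Outcome Measures takes a 0.6-point reduction as meaningful. Under the Step 4 assumptions, the chance that the observed mean change reaches 0.6 is greatest at SD 1.2:

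- n = 55: z = (0.6 − 0.2)/(1.2/√55) = 0.4/0.162 = 2.47, probability 0.7%
- n = 44: z = 0.4/(1.2/√44) = 0.4/0.181 = 2.21, probability 1.4%

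**The case against.** The strongest reply is that the plan is open about its comparison. The hypotheses are stated relative to baseline, the endpoint is a baseline-to-follow-up difference, the tests are paired, and the Analytic Plan says the data serve to refine the program before a randomized trial examines efficacy. This stands, and it is why the point is minor. It does not correct the spillover sentence or the four labels, which conflict with that framing.

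A second reply is that spillover is said to be minimal and that staff will not influence pain care. That concerns the size of the bias. It does not fix its sign, and the support cited comes from a different trial.

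A third reply is that the regression can be fitted. In a stacked layout it can, so a reader should not infer that the model fails under every reading. The fault is an unspecified layout and a term that is either inestimable or merely time.

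A fourth reply concerns the sources of background change. The weekly calls prompt module completion and answer questions about content, so they could be counted as part of the intervention package. The text available also shows no pain-score entry threshold that would make regression to the mean certain. Both are fair, so corrected wording should say that the change may include these components.

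**Conclusion.** The statement on spillover is wrong as written, and the treatment-effect labels and the indicator need correcting. The point is minor: it affects how the Phase II result is interpreted and one model term. The conclusion rests on the single-arm design and on algebra, not on the assumed figures.

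Three stronger readings are tempting, and the documents do not support them.

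- *The pilot needs a control arm.* A single-arm feasibility study is a legitimate choice, and efficacy is explicitly deferred.
- *The result will be inflated.* The direction is unknown; background worsening would shrink the change.
- *The 23% to 68% significance probabilities at n = 55 measure the damage.* They depend on an assumed SD and an assumed 0.2-point background change. Under the same assumptions the observed mean reaches 0.6 points about 1% of the time at most (0.7% with 55 followed, 1.4% with 44). The plan does not say whether 0.6 applies to the mean or to individuals, so this comparison is also only indicative.

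**What to change.** 1. **Usual Care paragraph.** Replace the conservative-estimate sentence with: *Phase II has no comparison arm; the observed change may include changes in usual care, natural course, regression to the mean, staff contact and the change from in-person to online assessment, and may overstate or understate the effect of VPMRC.*
2. **Analytic Plan, Phase II.** Replace the four treatment-effect phrases with *mean change from baseline to week 10 under UC+VPMRC*, and report the primary estimate with a 95% CI.
3. **Analytic Plan, Phase II.** Replace the indicator sentence with: *The change score will be regressed on centred baseline covariates; the intercept is the mean change and no treatment indicator is included.* State that in complete cases adjustment does not move this estimate. State also that the regression, like the ANCOVAs already planned, describes which baseline characteristics are associated with change and does not control for background change.

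The cost is text only. Sample size, visits and the paired test are unchanged. The downside for the sponsor is a less favourable interpretation of the Phase II result.
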